8.6.3 Analysis of secondary endpoints

All secondary analyses will be performed using the FAS, unless otherwise stated. The response-type endpoints [REDACTED] will be analyzed based on the methods described for ACR20 in primary analysis. Continuous endpoints [REDACTED]

will be analyzed based on an MMRM analysis that includes the fixed effects of treatment, visit, treatment by visit interaction, prior anti-TNF use [REDACTED] Baseline weight [REDACTED] and Baseline value. Due to [REDACTED] Tildrakizumab and placebo group switching [REDACTED] Tildrakizumab [REDACTED], the comparisons between active drug and placebo will not be

Statistical Analysis Plan (SAP)

performed for the secondary endpoints collected after [REDACTED]. Response-type and continuous endpoints after [REDACTED] will be summarized descriptively. In addition, proportion of subjects who require adjustment of background therapy at [REDACTED] be presented with descriptive statistics.

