4.2 Secondary efficacy endpoints [REDACTED]

The secondary efficacy endpoints of this study are:

Parts 1 and 2

- The proportion of subjects who achieve ACR20 [REDACTED]
- The proportion of subjects who achieve ACR50 [REDACTED]
ACR50 will be derived similarly as for ACR20 [REDACTED]
- The proportion of subjects who achieve ACR70 [REDACTED]
ACR70 will be derived similarly as for ACR20 [REDACTED]
- Change from Baseline in the individual components of ACR response at [REDACTED]
 - Tender joint counts [REDACTED]
 - Swollen joint counts [REDACTED]
 - PGA of disease activity (VAS)
 - PtGA of disease activity (VAS)
 - Patient's pain assessment (VAS)
 - Patient's self-assessed disability (HAQ-DI) [REDACTED]
 - Acute-phase hsCRP
 - ESR
- The proportion of subjects who require adjustment of background therapy [REDACTED]
- The proportion of subjects who achieve a DAS28-CRP [REDACTED]

The DAS28-CRP is a composite score derived from examination of the [REDACTED] for swelling and tenderness, CRP level, and patient global health assessment.

DAS28-CRP takes into account the following items:

- TJC28: [REDACTED]
- SJC28: [REDACTED]
- CRP: [REDACTED]
- GH: [REDACTED]

[REDACTED]
[REDACTED]

Statistical Analysis Plan (SAP)

If any of the components is missing, DAS28-CRP will be missing.

- The proportion of subjects who achieve MDA criteria at [REDACTED].

A psoriatic arthritis patient is defined as having a Minimal Disease Activity (MDA) response [REDACTED] when the patient meets [REDACTED] of the [REDACTED] following criteria: 1) tender joint count [REDACTED]; 2) swollen joint count [REDACTED] 3) PASI score [REDACTED] or BSA [REDACTED] 4) patient Arthritis Pain (VAS) [REDACTED]; 5) patient's global arthritis assessment [REDACTED] [REDACTED]; 6) HAQ-DI score [REDACTED]; 7) tender enthesal points [REDACTED] [REDACTED]

If there are sufficient non-missing components to determine whether the MDA is a response or non-response, then MDA is not missing. If the available non-missing components are not sufficient to determine the response status of MDA then it is considered missing.

- Change from Baseline in LDI and LEI at [REDACTED]

The Leeds dactylometer is a validated tool for assessing dactylitis. The dactylometer is used to measure the circumference of the base of the affected digit and is compared to the contralateral digit. [REDACTED]

[REDACTED] The final score for each digit is calculated and recorded on the CRF page, [REDACTED]

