The LEI examines tenderness at 6 sites: [REDACTED]

[REDACTED]. For each enthesal site, assessment is made of the adjacent joint in terms of tenderness and soft-tissue swelling, [REDACTED]. LEI is the number of sites in which enthesitis is present. The LEI score range is [REDACTED]. A missing assessment (ie, no box checked) or not assessed (ie, NOT DONE box checked) for any site will result in the LEI score being coded as missing.

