4.3 Exploratory endpoints

The exploratory endpoints of this study are:

Parts 1 and 2:

- [REDACTED]
[REDACTED]

A subject's PASI is a measure of overall PsO severity and coverage. PASI consists of 2 major steps: 1) calculating the BSA covered with lesions and 2) assessment of the severity of lesions.

- Body surface area involvement (%BSA): [REDACTED]

[REDACTED]

Statistical Analysis Plan (SAP)

- Lesion severity: The basic characteristics of psoriatic lesions – erythema, induration and scaling – provide a means for assessing the severity of lesions.

In each area, the sum of the intensity rating scores for erythema, induration and scaling is multiplied by the score representing the percentage of this area involved by psoriasis, multiplied by a weighting factor [REDACTED] The sum of the numbers obtained for each of the four body areas is the PASI.

The PASI combines the assessment of the intensity of lesions and the area affected into a single score in the [REDACTED] The PASI evaluation will only be conducted for subjects with moderate disease [REDACTED]

PASI75/90/100 is defined as at least 75%, 90%, and 100% reduction from baseline in PASI total score, respectively.

- SF-36 at measured time points ([REDACTED])
- PsAID questionnaire at measured time points

The PsAID questionnaire is a self-reported tool that assesses the impact of PsA on people's lives. The questionnaire assesses 9 items: pain, fatigue, skin problems, work and/or leisure activities, functional capacity, discomfort, sleep disturbance, coping, and anxiety, fear and uncertainty ([REDACTED]). The PsAID is calculated based on the 9 item ratings.

Statistical Analysis Plan (SAP)

If one of the items has missing value for rating, it will be imputed with the mean values of the ratings for the rest 8 items. The PsAID will be calculated with above formula. [REDACTED]

- ACR20, ACR50, ACR70, the components of ACR, DAS28-CRP, MDA, LDI, and LEI at other measured time points

[figure not shown]
Part 3:

ACR20, ACR50, ACR70, the components of ACR, LDI, LEI, PASI, and HAQ-DI at measured time points

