6 ANALYSIS POPULATIONS

6.1 Full Analysis Set (FAS)

The FAS will include all randomized subjects who have received at [REDACTED] of IMP (tildrakizumab or placebo). Analyses will be based on randomized treatment.

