8.6.4 Analysis of exploratory endpoints

The response-type endpoints (PASI 75/90/100) up to [REDACTED] will be analyzed based on the CMH methods described for ACR20. Continuous endpoints ([REDACTED] up [REDACTED] will be analyzed based on an MMRM analysis as described for secondary endpoints. Response-type and continuous endpoints after [REDACTED] will be summarized descriptively.

In addition, there will be sub-groups of patients in Part 3 who either did or did not receive any new therapy for PsA and these will be analyzed separately for ACR20, ACR50, and ACR70.

All the exploratory analyses will be based on the FAS except PASI, which will be based on the subjects in █ who have baseline █

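### Change from baseline in LEI is analysed in the whole FAS, so subjects without enthesitis at baseline dilute the estimate; LDI is affected only if absence of dactylitis scores 0

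*SAP*

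**What the plan says.** Section 4.2 lists "Change from Baseline in LDI and LEI at" certain visits (redacted) as a secondary endpoint, with no visible restriction to subjects who have dactylitis or enthesitis at baseline. Section 8.6.3 sets the population: "All secondary analyses will be performed using the FAS, unless otherwise stated". Section 6.1 defines that set by randomisation and dosing ("The FAS will include all randomized subjects who have received at" a redacted minimum of IMP), not by disease domain.

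Section 4.3 makes the same instruments exploratory at the remaining visits: "ACR20, ACR50, ACR70, the components of ACR, DAS28-CRP, MDA, LDI, and LEI at other measured time points". For these, section 8.6.4 says "All the exploratory analyses will be based on the FAS except PASI, which will be based on the subjects in" a redacted set with a baseline condition. PASI is the only exception named.

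On scoring, section 4.2 examines 6 sites and says "LEI is the number of sites in which enthesitis is present". For dactylitis it says "The dactylometer is used to measure the circumference of the base of the affected digit"; much of the scoring detail that follows is redacted.

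On the model, the continuous secondary endpoints "will be analyzed based on an MMRM analysis that includes the fixed effects of treatment, visit, treatment by visit interaction, prior anti-TNF use", baseline weight and the baseline value. No baseline-by-treatment term is visible.

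**The concern.** A subject with no enthesitis at baseline has LEI = 0 and can only stay at 0 or get worse. In every arm such subjects contribute changes at or near zero. Averaged over the FAS, the difference between arms mixes the effect in subjects who had enthesitis with near-zero differences from those who did not.

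What is at stake is the meaning of the reported number. The same drug effect on existing enthesitis would look smaller in a trial that enrolled fewer affected subjects. A reader comparing dose arms, or this trial with another, could take a difference in case mix for a difference in effect.

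**Working it through.** The visible SAP gives no LEI effect, no prevalence of enthesitis and no sample-size figure, so there is nothing of the plan's own to reproduce.

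**Inputs from the SAP.** Population: FAS (6.1, 8.6.3, 8.6.4). LEI: number of affected sites out of 6 (4.2). Baseline value as a covariate (8.6.3). Two-sided alpha 0.05 (8.1).

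**Assumed inputs.** Share affected at baseline p = 0.2 to 0.7; 80 subjects per arm; effects and new-onset rates as stated below.

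**Step 1: the dilution.** Let d be the treatment difference among affected subjects and d0 the difference among unaffected subjects. Then

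FAS difference = p × d + (1 − p) × d0.

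Unaffected subjects cannot improve, so d0 is about 0 unless treatment changes new onset, and the FAS difference is about p × d. With d = 0.5 SD (assumed) it is 0.10, 0.15, 0.25, 0.30 and 0.35 SD at p = 0.2, 0.3, 0.5, 0.6 and 0.7.

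**Step 2: does baseline adjustment remove it?** Simulated LEI-like scores: affected subjects start at 1 to 6 sites with equal probability; each site resolves with probability 0.6 on active and 0.4 on control; 5% of unaffected subjects gain one site in either arm. The true d is −(0.6 − 0.4) × 3.5 = −0.70. Change was regressed on treatment and baseline at one visit, 2,000 runs per row.

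| p | FAS estimate | Affected-only estimate | Ratio | Power FAS | Power affected-only | Loss (points) |
|---|---|---|---|---|---|---|
| 0.2 | −0.135 | −0.700 | 0.19 | 43.0% | 50.1% | 7.1 |
| 0.3 | −0.211 | −0.718 | 0.29 | 67.8% | 71.6% | 3.8 |
| 0.5 | −0.350 | −0.706 | 0.50 | 89.6% | 91.6% | 2.0 |
| 0.6 | −0.424 | −0.710 | 0.60 | 95.0% | 96.2% | 1.2 |
| 0.7 | −0.485 | −0.694 | 0.70 | 96.4% | 97.0% | 0.6 |

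The ratio tracks p closely. Baseline as a main effect does not remove the dilution.

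A separate LEI simulation with 8% new onset among unaffected subjects and a smaller effect (about −0.63 among affected) gave FAS estimates of about −0.31 at p = 0.50 and −0.41 at p = 0.65. Power was 54% against 60%, and 72% against 75%.

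**Step 3: why power hardly moves.** If unaffected subjects add no variance, the FAS variance is p × SD², so the standardised effect is p × d / (√p × SD) = √p × d/SD. At p = 0.5 and d = 0.5 SD this is 0.35. The FAS then has n subjects per arm at √p × d/SD, and the subset has n × p at d/SD. Both give n × p × (d/SD)², hence the same power: 61% at 80 per arm. Only noise from unaffected subjects, or a gap in mean change that baseline does not explain, costs power.

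**Step 4: LDI.** The identity applies only if a subject with no affected digit is scored 0. If the score is missing, that subject has no baseline value, drops out of a baseline-adjusted model, and there is no dilution. The visible text does not settle which.

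The simulations use a single-visit ANCOVA, not the full repeated-measures model.

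**The case against.** The strongest defence is that the FAS analysis is a legitimate choice. It estimates the average change over all treated subjects, keeps everyone randomised and dosed, and captures new enthesitis, which an affected-only analysis leaves out. That stands: the FAS estimate is not biased for its own question. Section 8.4.2 also summarises baseline LEI and LDI, which shows some of the case mix, although the summary statistics for continuous variables in 8.1 do not include the number of subjects at 0.

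A second defence is redaction. The list of continuous endpoints in 8.6.3 is blacked out and could hold a restriction. That cannot be excluded, but it is unlikely: 8.6.4 names PASI as the sole exception for an exploratory list that includes LDI and LEI. A restriction in 8.6.3 alone would give the same instrument different populations at different visits.

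Three stronger readings are tempting, and the SAP does not support them.

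- A reader might infer that restricting PASI shows the authors recognised dilution there and overlooked it here. Section 4.3 says PASI is assessed only in subjects with moderate disease, so the restriction may simply follow who is measured. PASI75/90/100 are also percent reductions, which are undefined at a baseline of zero.
- A reader might infer that the model is invalid because unaffected subjects vary less than affected ones. The unstructured matrix in 8.6.1 lets variance differ by visit, though no grouping by baseline status is visible. No consequence for type I error or coverage has been shown.
- A reader might infer a large loss of power. With the baseline adjustment that the plan specifies, the calculations do not show one.

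**Conclusion.** The point holds for LEI as a matter of interpretation, not as an error. As far as the visible text shows, the reported difference will be about the affected share times the effect among affected subjects: roughly 0.2 to 0.7 of that effect over the assumed range, and half of it at 50%. This rests on unaffected subjects showing no treatment difference and on no restriction lying under the redactions. Power loss is about 1 to 7 points under the assumed inputs and is not the reason to act.

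For LDI the point is conditional on absence of dactylitis being scored 0. It would be wrong to assert it outright.

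LEI and LDI are secondary or exploratory endpoints, and the primary ACR20 analysis is unaffected. Priority is low to moderate.

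**What to change.** Before unblinding, add to 8.6.3 and repeat in 8.6.4: change from baseline in LEI will be analysed in FAS subjects with baseline LEI > 0, with the number of such subjects reported per arm. State in 4.2 how a subject with no affected digit is scored on the LDI. If the score is 0, apply the same rule with baseline LDI > 0. Keep the full-FAS analysis as supportive, and describe new onset in subjects with a baseline score of 0.

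The subset is defined by a pre-treatment value, so the comparison between randomised groups is preserved. The cost is SAP wording and a smaller n for these endpoints. With fewer subjects the unstructured matrix may fail to converge more often; the fallback structures in 8.6.1 already cover that.

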8.6.4 Analysis of exploratory endpoints

The response-type endpoints (PASI 75/90/100) up to [REDACTED] will be analyzed based on the CMH methods described for ACR20. Continuous endpoints ([REDACTED] up [REDACTED] will be analyzed based on an MMRM analysis as described for secondary endpoints. Response-type and continuous endpoints after [REDACTED] will be summarized descriptively.

In addition, there will be sub-groups of patients in Part 3 who either did or did not receive any new therapy for PsA and these will be analyzed separately for ACR20, ACR50, and ACR70.

All the exploratory analyses will be based on the FAS except PASI, which will be based on the subjects in █ who have baseline █

8.7 Safety analyses

Safety analyses will be conducted on the Safety Analyses Set (treated subjects) and will be performed for all safety variables specified below.

All safety data will be summarized by treatment group.

The safety analyses of changes from baseline to a specific time point in safety variables (e.g., laboratory parameters, vital signs, and ECG) will only include subjects from the Safety Analysis Set who have data available for both the baseline and the time point under consideration unless otherwise specified.

No statistical test will be performed.

8.7.1 Adverse events

All AEs will be classified by Primary System Organ Class (SOC) and Preferred Term (PT) according to the most recently available version of the MedDRA dictionary.

Statistical Analysis Plan (SAP)

In summaries by SOC and PT, adverse events will be sorted within each SOC and PT in alphabetical order. In summaries by PT, AEs will be sorted within each PT in alphabetical order.

Details for imputing missing or partial start dates of adverse events are described in [REDACTED].

TEAEs are defined as any AE occurring or worsening on or after the first dose of IMP. AE summary tables will be presented for TEAEs only and will include the following:

- All TEAEs
- Related TEAEs (AE will be defined as related if causality is possibly, probably, or certain)
- TEAEs by maximum severity
- TEAEs leading to discontinuation
- Serious TEAEs
- TEAEs leading to death.

An overall summary for the categories above will be prepared by study part, treatment group and overall. A TEAE in [REDACTED] is defined with the event start date on/after the [REDACTED] but before [REDACTED] date of IMP or on/before the last dose date of IMP if the subject discontinues treatment before [REDACTED]. A TEAE in [REDACTED] defined with the event start date on/after [REDACTED] dosing date but on/before the [REDACTED]. A TEAE in [REDACTED] is defined with the event start date after the last dose date of IMP.

In addition, all TEAEs will be summarized by study part [REDACTED] SOC, PT and treatment group using frequency counts and percentages (i.e., number and percentage of subjects with an event).

Where a subject has the same adverse event, based on preferred terminology, reported multiple times in a specific study part, the subject will only be counted once at the preferred terminology level in adverse event frequency tables.

Where a subject has multiple adverse events within the same system organ class in a specific study part, the subject will only be counted once at the system organ class level in adverse event frequency tables.

When reporting adverse events by intensity, in addition to providing a summary table based on the event selection criteria detailed above, summary table will also be provided based on the most intense event - independent of relationship to study treatment.

[REDACTED]

[REDACTED]

[REDACTED]

[REDACTED]

[REDACTED]

[REDACTED]

Statistical Analysis Plan (SAP)

In addition, a listing containing individual subject adverse event data for TEAEs leading to discontinuation from study, Serious TEAEs, TEAEs leading to death, [REDACTED] will be provided separately. All AEs, including pre- and post-treatment AEs, will be presented in an individual subject data listing.

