6.5 ADA Evaluable Set

The ADA Evaluable Set will include all subjects in the Safety Analysis Set who have at [REDACTED] [REDACTED] Assay results from the placebo portion of the trial will not be included in the immunogenicity assessment, although subjects who are randomized to [REDACTED] will be included in the assessment if they are treated with tildrakizumab in Part 2.

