8.3 Subject disposition

The number of subjects in the following categories will be summarized overall and by treatment group:

- Randomized
- Full Analysis Set (FAS)
- Per Protocol Analysis Set (PPAS)
- Safety Analysis Set
- PK Analysis Set
- ADA Evaluable Set

The number and percentage [REDACTED] of subjects in each of the following disposition categories will be summarized overall and by treatment group:

- Completed treatment at [REDACTED]
- Prematurely discontinued the treatment and the reasons for discontinuation
- Completed study (i.e., completed the wash-out period)
- Prematurely discontinued the study and the reason for discontinuation

A listing will be provided for subjects who discontinued treatment or who discontinued study with reasons for discontinuation.

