8.7.2 Clinical laboratory evaluations

For the purposes of summarization in both the tables and listings, all laboratory values will be presented in SI units. If a lab value is reported using a nonnumeric qualifier [REDACTED] [REDACTED], the given numeric value will be used in the summary statistics, ignoring the nonnumeric qualifier.

Clinical laboratory parameters observed values and changes from Baseline will be summarized at each scheduled visit. Shift tables from baseline to post-baseline in lab parameters for each treatment group during ■■■ will be displayed by visit.

Statistical Analysis Plan (SAP)

Values outside the [REDACTED]
[REDACTED]
[REDACTED]

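### For subjects who stop IMP in the first part, TEAEs starting after the last dose date leave the first-part tables, the only ones with concurrent placebo

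*SAP*

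**What the plan says.** SAP section 8.7.1 counts as treatment-emergent any AE that begins or worsens from the first dose onward, with no visible end limit. It then divides TEAEs among three study parts by start date. The part labels and boundary dates are redacted.

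- **First-defined part.** It runs until just before a later IMP date. For a subject who stops before a redacted point, it runs only "on/before the last dose date of IMP if the subject discontinues treatment before" that point.
- **Last-defined part.** A TEAE in this part "is defined with the event start date after the last dose date of IMP". No exception is visible for subjects who stopped in the first part.

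The parts determine the tables: "An overall summary for the categories above will be prepared by study part, treatment group and overall". The categories include TEAEs leading to discontinuation, serious TEAEs and TEAEs leading to death. The SOC and PT tables are also by study part.

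Three places indicate which part has concurrent placebo. Section 3.1 describes one placebo-controlled period, followed by a double-blind follow-up period and wash-out. Section 6.5 says that subjects randomized to a redacted group "will be included in the assessment if they are treated with tildrakizumab in Part 2". Section 8.6.3 refers to the placebo group switching and says that, for secondary endpoints after a redacted time, "the comparisons between active drug and placebo will not be" made.

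**The concern.** The rule treats two kinds of subject differently within one part. A subject who continues contributes the whole interval after the last first-part injection. A subject who stops contributes nothing after the day of the last injection.

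The difference is tied to the outcome. If an AE starts on a day after an injection and the next injection is withheld because of it, that earlier injection becomes the last dose. The AE then falls outside the first part because it ended treatment. The same applies to a serious or fatal TEAE that starts after the last dose date. Events between two injections that were both given stay in the first part, including serious ones.

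Section 8.7 plans no statistical tests on safety data, so the displayed counts are the safety result. If the first part is the only one with concurrent placebo, the categories that matter most for tolerability are counted incompletely in the one comparison that can be read against placebo.

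**Working it through.** **Reading the windows.** The labels are redacted, so the mapping is an inference. Three windows are given in order, and the last is anchored on the last dose of IMP. That fits Parts 1, 2 and 3, with Part 1 the placebo-controlled part. On this reading:

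| Start of TEAE | Subject continues | Subject stops in first part |
|---|---|---|
| On or before the last first-part dose date | First part | First part |
| After that date, before the next part's first dose | First part | Last part |

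**No stated figure to reproduce.** Section 5 (sample size) shows no content in the public copy, and the SAP gives no dosing interval, stopping rate or AE rate. The list of abbreviations names 4-week and 12-week intervals. I therefore use L = 28 and L = 84 days as assumptions. Section 6.1 counts placebo as IMP, so one common interval in all arms is a working assumption.

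**Days not counted.** For a subject who stops after k doses given every L days, the first-part window is L(k−1) + 1 days. With one further interval counted, it would be Lk days. The difference is L − 1: 27 days at L = 28 and 83 days at L = 84. As a share of the longer window:

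- L = 28: 27/28 = 96% (k = 1), 27/56 = 48% (k = 2), 27/84 = 32% (k = 3), 27/168 = 16% (k = 6)
- L = 84: 83/84 = 99% (k = 1), 83/168 = 49% (k = 2)

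**Share of AEs leading to discontinuation that move.** Assume that onset U is uniform over the interval (0, L) and that the lag T from onset to the stop decision is exponential with mean m. The event moves if it starts after the dosing day and the decision comes before the next injection:

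P(U > 1 and U + T < L) = (L − 1)/L − (m/L)[1 − exp(−(L − 1)/m)]

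Example, L = 28 and m = 7: 27/28 − (7/28)(1 − e^(−27/7)) = 0.964 − 0.25 × 0.979 = 0.720.

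| Mean lag m (days) | L = 28 | L = 84 |
|---|---|---|
| 3 | 86% | 95% |
| 7 | 72% | 90% |
| 14 | 54% | 82% |
| 28 | 35% | 67% |

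A simulation of 4,000,000 draws per cell agreed with the formula to within 0.0003. If onsets cluster on dosing days, the shares are lower.

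**Effect on an arm comparison with equal shares.** Displayed risk = true risk × (1 − share). Take assumed true risks of 6% (active) and 4% (placebo), a difference of 2.0 points and a ratio of 1.5:

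- Share 0.720: 6 × 0.280 = 1.7% against 4 × 0.280 = 1.1%, difference 2 × 0.280 = 0.6 points
- Share 0.346: 6 × 0.654 = 3.9% against 4 × 0.654 = 2.6%, difference 2 × 0.654 = 1.3 points

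The ratio stays at 1.5. The counts and the risk difference shrink.

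**Serious and fatal TEAEs, at L = 28.** If 10% to 50% of serious TEAEs are followed by no further dose (assumed), 0.10 × 27/28 = 10% to 0.50 × 27/28 = 48% move. For fatal events of acute onset spread evenly over days, 27/28 = 96% move.

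**All TEAEs.** Only early stoppers can lose first-part events. The fall in the percentage of subjects with any first-part TEAE is therefore at most the percentage who stop in that part: 2, 5 or 10 points if 2%, 5% or 10% stop.

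**The case against.** **Nothing is lost from the data.** This stands. The events remain TEAEs and are counted in the last-part tables. Section 8.7.1 adds: "All AEs, including pre- and post-treatment AEs, will be presented in an individual subject data listing". Separate listings cover serious and fatal TEAEs and those leading to discontinuation from study. Section 8.3 summarizes by treatment group the subjects who "Prematurely discontinued the treatment and the reasons for discontinuation". Visit-based summaries are untouched, as in section 8.7.2: "Clinical laboratory parameters observed values and changes from Baseline will be summarized at each scheduled visit".

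None of these restores the comparison. The last part also holds subjects who reached wash-out after Part 2, and section 8.6.4 shows that some subjects in Part 3 receive new PsA therapy. The disposition table has no visible split by part and no SOC, PT, severity or seriousness. If the word overall in section 8.7.1 means a total across parts, that total includes time after the placebo switch.

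**Redaction.** This stands as a limit. Blocks at the end of the section 8.7.1 table description are blacked out and could hold another AE table. Section 8.1 sets two treatment-group display formats whose contents are also hidden. No visible table offsets the rule.

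**Any event after the final injection is excluded.** A reader might infer this, but the text does not support it. An event that starts later on the day of the final injection is on the last dose date and stays in the first part.

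**The comparison with placebo is biased in a known direction or could reverse.** A reader might infer this too. A reversal needs different shares moved in the two arms, for example through markedly different lags to stopping. Section 3.2.2 keeps sites and subjects blinded, and the documents give no basis for such a difference.

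**Descriptive safety only, primary endpoint untouched.** True, and the effect on all TEAEs is small if few stop. But with no tests planned, the tables themselves carry the conclusion.

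**Conclusion.** The point holds as an undercount by rule, and it should be fixed. In the first-part tables, TEAEs leading to discontinuation, fatal TEAEs and serious TEAEs with no further dose are counted only if they start on or before the last dose date. On the visible text, no other table gives these counts against concurrent placebo.

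The size is illustrative, and every input is assumed: about 35% to 86% of AEs leading to discontinuation move at a 28-day interval, and about 67% to 95% at 84 days, for mean lags from 28 down to 3 days. With equal shares in all arms, the risk ratio is preserved while the counts and the risk difference shrink. No direction of bias between arms and no change of sign is claimed. The conclusion rests on reading the first-defined part as the placebo-controlled part and on no redacted table already covering the gap. Confidence is medium for those two reasons.

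**What to change.** Keep the present rule and label its output as an on-dose table. Add a first-part table of all TEAEs, TEAEs leading to discontinuation, serious TEAEs and fatal TEAEs. For early stoppers it should also count events that start within one pre-specified window after the last dose. The window must be identical in all arms, and the sponsor should justify its length.

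The window must lie within the time in which AEs are collected after stopping. Section 3.1 requires an assessment after IMP is stopped (except on withdrawal of consent), but its details are redacted and it does not by itself show continuous AE collection. The sponsor should confirm this. If a redacted table already counts these events, section 8.7.1 should refer to it and nothing more is needed.

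The cost is a change to the SAP wording, one derivation in the AE dataset and one added set of tables. No new data are needed if the window lies within the collection period. The downside belongs in a footnote: some events off treatment, or after other therapy has begun, will be counted in the first part.
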